11.2 Deaths

Adverse events and the principal cause of death will be coded using MedDRA version 23.1.

Deaths will be summarized by MedDRA primary system organ class and preferred term of the principal cause of death.

11.3 Vital signs

Vital signs measurements (including blood pressure, temperature, respiratory rate, pulse rate, SpO₂, and ratio of SpO₂/FiO₂) and change from baseline values will be summarized over time with n, mean, SD, and median, minimum, and maximum. Summaries will be presented by treatment and overall.

Vital signs information will also be provided in a data listing.

11.4 Clinical safety laboratory

Haematology, coagulation, and biochemistry

The following statistical analyses will be presented:

- Quantitative data will be examined using descriptive statistics (number of patients with data, mean, SD, median, minimum, and maximum) of actual values and changes from baseline to each visit over time.
- Qualitative data based on reference ranges will be described according to the categories (i.e., Low, Normal, High).
- Shift tables showing changes with respect to the normal range between baseline and each timepoint as well as the worst value at any post-baseline visit.

A separate listing will also be provided. Laboratory values that are outside the normal range will also be flagged in the data listings, along with corresponding normal ranges.

Urinalysis

The following statistical analyses will be presented only at screening:

QMS Document Name: Statistical Analysis Plan	Page 24 of 27
QMS No (include version ref): STF-015-GL.02	Document date: 09JUL2019
CONFIDENTIAL	

- Quantitative data will be summarized using descriptive statistics (number of patients with data, mean, SD, median, minimum, and maximum) of actual values.
- Qualitative data based on reference ranges will be described according to the categories (i.e., Low, Normal, High).

11.5 ECG

Baseline and changes from baseline in RR, PR, QT, QTc, QTcF, QRS and HR will be summarized at each timepoint using descriptive statistics Descriptive statistics by treatment and timepoints (mean, SD, 25th percentile, median, 75th percentile, minimum, and maximum)

Number and percentage of overall interpretation of electrocardiogram (ECG) (i.e., normal, abnormal not clinically significant, abnormal clinically significant) and shift from baseline will be summarized by treatment and overall.

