#### **Investigational Product, Dose, Route of Administration, and Regimen:**

**Test product:** Asapiprant, a DP1 antagonist, will be provided as a 50 mg tablet for oral use

**Placebo:** Matching tablet without active drug

Two 50 mg tablets of asapiprant (100 mg) or matching placebo will be taken immediately after screening evaluation, confirmation of eligibility, and randomization on Day 1, and within 30 minutes of eating. Time of dosing in relation to meal will be documented. Subjects will continue dosing for 14 days, including if they are discharged or if the subject progresses to RF. Subjects taking nothing by mouth (NPO) or not being fed through an NG tube will take study medication at approximately the same time they received prior daily doses.

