a Visit procedures at time of discharge will occur at the date of the dosing visit if visit occurs prior to Day 14, will occur at the Day 14 visit if occurs on Day 14, or will occur on the date of discharge after dosing if after Day 14. This visit is not required if discharge occurs within 2 days after Day 14. If discharge occurs on Day 4, the Day 5 assessments of abbreviated physical exam, safety labs, trough and peak PK, and blood for inflammation markers will not be collected if they were completed as part of the discharge procedures on Day 4.

b Same-day medical record examinations may be used for study purposes to reduce the possible exposure of site staff to COVID-19 risk. Physical examinations may be conducted as standard of care examinations. Abbreviated physical examinations may be conducted by qualified home health care providers or remote/telemedicine visits. Abbreviated physical examinations that cannot be performed at day 5 may be performed up to Day 7.

c WHO Ordinal Scale is derived from subject's oxygen supplementation requirements, hypotension or need for vasopressors, need for renal dialysis, and activity limitations for outpatients.

d Trough PK samples collected within 30 minutes prior to dose.

e ECG and PK sampling to be performed on last day of study treatment if subject remains hospitalized through Day 14. ECG and PK samples are not required on Day 14/EOT if subject is discharged to home before Day 14.

f ECG and PK sampling to be performed at the time of hospital discharge if subject is discharged prior to Day 14. ECG and PK sampling are not required at time of discharge if discharge occurs after the Day 14 visit.

g Peak PK samples collected 3-6 hours after dose.

h Done every other day until 2 qualitative test done at local laboratory is negative. After qualitative test is negative, do viral titer nasopharyngeal testing only on Day 28. For outpatients, scheduled viral titer tests may be skipped on Saturday or Sunday and/or may be skipped if dry ice shipments are not available. In the Saturday or Sunday situation Day 13 tests should be done on the following Monday.

i Safety labs collected within 48 hours prior to consent as part of standard of care can be used to confirm eligibility.

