4.5 Visit Windows

The following table outlines the analysis visits that data will be mapped to for analysis of efficacy, safety and pharmacodynamics data collected during the study. If after mapping, multiple data points share the same analysis visit, the data point closest to the expected study visit will be used. If there is a tie, the earlier of the visits will be used.

Study Visit	Analysis Visit	Analysis Window
Screening	Screening	-3 to -1
Days 1 – 13	Days 1 – 13	0
Days 14	Days 14	+2 day
Day 28 Follow-up	Day 28	± 2 day
Day 57 Phone Follow-up Visit	Day 57	± 4 day

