	3	32
	4	36
	5	40
	>=6	44
Nasopharyngeal catheter	1	25
	2	30
	3	35
	4	40
	5	50
	>=6	60
Face mask (simple mask)	<5	Follow nasal cannula
	5	40
	6-<7	50
	>=7	60

Face mask with reservoir (non-rebreather face mask)	<6	Follow nasal cannula
	6	60
	7	70
	8	80
	9	90
	10	95
	>10	100
Venturi mask	1	22
	2	24
	3	26
	4	28
	6	31
	8	40
	10	50
	>10	60

In case of fractional value of flow rate (0.5, 1.5, 2.5, 3.5, 4.5), $\text{FiO}_2 = (\text{Oxygen Flow Rate} * 4) + 20$ to avoid rounding.

- Length of hospital stay, after start of study treatment, in days: which will be defined as duration from date of randomization to the date of first discharge.

11 Safety

All safety endpoints will be analyzed using the SAF under received treatment based on the data observed. No missing data will be imputed.

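### ECG interval changes after Day 2 are tabulated separately by discharge status, and no planned by-arm summary combines each subject's later on-treatment ECG

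*SAP*

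**What the plan says.** The ECG row of protocol Table 1 has entries at Day 1, Day 2, Day 14/end of treatment and discharge, and nowhere else. Footnote e covers the Day 14 recording: "ECG and PK sampling to be performed on last day of study treatment if subject remains hospitalized through Day 14", and "ECG and PK samples are not required on Day 14/EOT if subject is discharged to home before Day 14". Footnote f covers everyone else: "ECG and PK sampling to be performed at the time of hospital discharge if subject is discharged prior to Day 14". It also waives the discharge recording when discharge follows the Day 14 visit. Dosing does not stop at discharge. The synopsis says: "Subjects will continue dosing for 14 days, including if they are discharged or if the subject progresses to RF".

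SAP 11.5 plans two ECG outputs. For intervals and heart rate: "Baseline and changes from baseline in RR, PR, QT, QTc, QTcF, QRS and HR will be summarized at each timepoint", by treatment. For overall interpretation, counts and "shift from baseline will be summarized by treatment and overall", with no timepoint and no rule for choosing among a subject's ECGs. Protocol 8.8 likewise summarizes ECG findings by treatment group and visit.

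SAP 4.5 governs the mapping: "The following table outlines the analysis visits that data will be mapped to for analysis of efficacy, safety and pharmacodynamics data". The visits listed are Screening, Days 1 to 13 (window 0), Day 14 (+2), Day 28 (±2) and Day 57 (±4). SAP section 11 adds: "All safety endpoints will be analyzed using the SAF under received treatment based on the data observed. No missing data will be imputed".

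**The concern.** The Day 14 and discharge ECGs are in effect alternatives, and which one a subject has depends on when that subject leaves hospital. Length of hospital stay is a secondary efficacy endpoint, so the drug is meant to influence what sorts subjects into one ECG group or the other. A table by timepoint then shows, at Day 14, mainly subjects who stayed in hospital and, elsewhere, those who left. Neither is a comparison of the randomized arms. Subjects absent at Day 14 are not off treatment; they are still dosed but need not be recorded.

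At stake is how far an ECG interval shift after repeated dosing, or its absence, can be read from the report. Each subset is smaller than the data collected allow, and the two arms' subsets may differ in severity. Day 2 is the last timepoint at which the schedule asks for an ECG from everyone on the same day.

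**Working it through.** No figure stated in the plan is in dispute, so the check is a cross-reading followed by arithmetic on labelled assumptions.

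**Who has which ECG after Day 2**

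- Still hospitalized through Day 14: Day 14/EOT ECG (footnote e), with no discharge ECG required later (footnote f).
- Discharged on Day 14: procedures are done at the Day 14 visit (footnote a).
- Discharged earlier: ECG at discharge (footnote f), Day 14 ECG waived (footnote e).
- Study drug stopped early: end-of-treatment evaluations are done at that point (protocol 4.6), so an EOT ECG may fall on another day.
- Dead before either ECG, or discharged by Day 2: no later ECG.

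With any discharge before Day 14, no single timepoint after Day 2 is scheduled to cover all treated subjects. SAP 11.5 defines no last or worst ECG value to bring the groups together. SAP 11.4 does plan a worst post-baseline value for laboratory shifts.

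**Precision**

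Inputs from the documents: 312 subjects randomized 1:1, so 156 per arm. The SAP addendum says enrollment stopped before the interim analysis, which was set at about 208 subjects, so 208/2 = 104 per arm is used as an assumed alternative. Inputs not in the documents: QTcF-change SD of 20 ms, and 10% to 40% of each arm still hospitalized at Day 14.

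Half-width of the 95% interval for the arm difference = 1.96 × 20 × √(2/n), with n per arm.

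| Still hospitalized | n of 156 | Half-width | n of 104 | Half-width |
|---|---|---|---|---|
| 10% | 15.6 | 14.0 ms | 10.4 | 17.2 ms |
| 40% | 62.4 | 7.0 ms | 41.6 | 8.6 ms |
| Pooled (all) | 156 | 4.4 ms | 104 | 5.4 ms |

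The pooled row assumes that every subject has a later ECG. Deaths and missing recordings would widen it somewhat.

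**Selection**

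Take the planning rates of respiratory failure (RF), 31% on placebo and 15% on asapiprant. As an illustration, assume that every RF subject and a fraction r of the others are alive and in hospital at Day 14. Day 14 coverage = p + (1 − p)r, and the RF share of those measured = p divided by that coverage.

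- r = 10%: placebo 0.31 + 0.69 × 0.10 = 37.9%, RF share 81.8%; asapiprant 0.15 + 0.85 × 0.10 = 23.5%, RF share 63.8%.
- r = 30%: placebo 0.31 + 0.69 × 0.30 = 51.7%, RF share 60.0%; asapiprant 0.15 + 0.85 × 0.30 = 40.5%, RF share 37.0%.

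If the drug worked as planned, the Day 14 groups would therefore differ between arms in both size and severity.

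**The case against.** The strongest reply is that these are descriptive tables. Protocol 8.4 intends no formal safety analysis. The protocol reports no toxicity to date and no known adverse events of special interest, and the ECGs are single investigator-read recordings. A clinically significant ECG change can be recorded as an adverse event, and it would then enter the by-arm tables through Day 57. All of this stands. A reader might infer that the Day 14 table is the drug's main cardiac safety result; nothing in the documents gives it that role.

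A reader might also infer from SAP 4.5 that discharge ECGs will be scattered over Days 3 to 13. That is only one reading. SAP 11.6 lists discharge as an examination timepoint, and SAP 2.3 and protocol 8.8 name it for safety laboratory tests. A nominal discharge table for ECGs is therefore quite possible, and table specifications are in a separate document. The concern survives either way, because a discharge table beside a Day 14 table still divides subjects by a post-randomization outcome.

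Nor do the documents support calling the Day 14 group the sickest subjects. It includes those discharged on Day 14, may include early stoppers of study drug, and could include a discharged subject recorded voluntarily, since the ECG is waived and not forbidden. The group is selected, but not purely by severity.

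The shift summary has no stated timepoint and may already pool ECGs; the SAP does not say.

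Finally, a pooled ECG does not restore a comparison at fixed exposure. It falls after anything from a few doses to the full course, and that may differ by arm. This is a real limit, and it is why the derived value should be added and not substituted for the by-timepoint tables.

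**Conclusion.** The point holds as a gap in the analysis plan more than in data collection. After Day 2 the scheduled ECGs are split by discharge status, no planned by-arm interval summary uses all treated subjects with a later ECG, and the shift summary leaves its ECG unspecified. No error rate and no efficacy conclusion is affected.

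The size is conditional. Under the assumed SD and in-hospital fractions, the Day 14 half-width is roughly 1.6 times (7.0/4.4) to 3.2 times (14.0/4.4) the pooled one, and the ratio is the same at 104 per arm. The absolute values at 156 per arm are probably optimistic, given that enrollment stopped before the interim analysis. The documents give neither a discharge rate nor a QTcF SD, so the direction is firm and the figures are illustrative.

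The change is worth making because it is cheap and uses ECGs the protocol already schedules. It does not require dropping the Day 14 table.

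**What to change.** In SAP 4.5 and 11.5:

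1. Define one derived last on-treatment ECG per subject: the Day 14/EOT ECG, including the EOT ECG of subjects who stop study drug early; otherwise the discharge ECG. Count subjects with no ECG after Day 2 by arm, without imputing.
2. Summarize change from baseline in the intervals, and shift in overall interpretation, by arm in the Safety Set at this derived visit, alongside Day 2 and the existing by-timepoint tables.
3. Show days of dosing at the derived ECG by arm.
4. State how a discharge ECG is mapped, and which ECG the shift summary uses.
5. Label the Day 14-only and discharge-only tables as subsets selected by discharge status.
6. Optionally, add a worst post-baseline value, as SAP 11.4 does for laboratory data.

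The cost is SAP wording and table shells, with no new assessment. The downside is that exposure at the derived ECG varies and may differ by arm, so the summary must be read with item 3 beside it.

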11.6 Physical examination

A complete physical examination (PE) will be performed at Screening. After Screening, abbreviated physical examination will be performed at Days 5 and 14, at discharge, and at Day 28.

Number and percentage of result (normal, abnormal, not done) of full PE result at screening and post-baseline abbreviated PE result at each visit will be summarized by treatment and overall.

PE will be provided in a data listing by patient.

12 Other Analyses – please specify

The pharmacokinetic (PK) analyses will be described in a separate analysis plan.

For inflammation markers of COVID-19 infection, including but not limited to IL-6, CRP, IL-10, TNF- α , IFN- γ , IFN- α , IFN- γ , IP-10, MCP-1, and absolute lymphocyte count, summaries will be presented by treatment and overall using descriptive statistics. Both the observed value and the change from baseline value will be summarized.

13 Interim Analyses

An interim analysis for safety and primary endpoint will be conducted after the first approximately 208 patients complete assessments through the 28-day follow up (Day 28), approximately 14 days after the final dose of study drug. Unblinded interim analysis results will be reviewed by the independent and unblinded DMC for safety evaluation. Details of the roles/responsibilities of DMC members and each party, meeting schedule and intended activities are described in a separate DMC Charter.

Analysis of primary endpoint at the interim will follow as described in [section 10.1](#).

An α spend is not incorporated into the sample size to account for the interim, as there is no potential for stopping for superiority.

Efficacy analyses at interim analysis (IA) may yield Conditional Power (CP) results in the Mehta and Pocock promising zone (0.34, 0.90) (Mehta and Pocock, 2011). If so, to maintain the statistical power of the study and to avoid any type 1 error penalty, the Sponsor will consider the option of increasing the sample size (according to the rules provided by Mehta and Pocock), not to exceed N=624 (twice the planned sample size). For this planned IA, Z-score evidence based on logistic regression as [10.1](#)

QMS Document Name: Statistical Analysis Plan	Page 25 of 27
QMS No (include version ref): STF-015-GL.02	Document date: 09JUL2019
CONFIDENTIAL	

at the IA of between $Z=1.41$ and 2.21 would define the promising zone and opportunity for BioAge to expand the study. For example, if at IA, $Z=1.8$ ($CP=0.66$), then to maintain the power at 0.90 the study could be expanded from 312 subjects to 500. For results in the Mehta and Pocock unfavorable zone, or in the favorable zone, the study will continue to conclusion at $N=312$ subjects.

14 Statistical Analyses for Safety Monitoring

The statistical analysis for safety monitoring is specified in a separate DMC charter.

15 References

1. Guideline on adjustment for baseline covariates in clinical trials, EMA/CHMP/295050/2013, 2015
3. Senn SJ. Covariate imbalance and random allocation in clinical trials. *Stat Med* 1989;8:467e75.
4. ICH Harmonised Tripartite Guideline E9, Statistical Principles for Clinical Trials, 1998
5. ICH Harmonised Tripartite Guideline E3, Structure and Content of Clinical Study Reports. 1996
6. ICH Harmonised Tripartite Guideline E6(R2), Guideline for Good Clinical Practice, 2018
7. ICH guideline E2F, Note for guidance on development safety update reports, EMA/CHMP/ICH/309348/2008, September 2010
8. Guideline on missing data in confirmatory clinical trials, EMA/CPMP/EWP/1776/99 Rev. 1, 2010
9. ICH E9 (R1) addendum on estimands and sensitivity analysis in clinical trials to the guideline on statistical 6 principles for clinical trials, Step 2b (Draft), EMA/CHMP/ICH/436221/2017, 2017
10. Mehta, C.R., and Pocock, S.J. (2011) Adaptive increase in sample size when interim results are promising: a practical guide with examples. *Stat Med* 40, 3267–3284.

QMS Document Name: Statistical Analysis Plan	Page 26 of 27
QMS No (include version ref): STF-015-GL.02	Document date: 09JUL2019
CONFIDENTIAL	

16 Addendum

Based on the following information and justifications, baseline WHO ordinal scale is removed from primary endpoint logistic regression:

- 1) enrollment stopped before interim analysis and all enrolled patients have passed Day 28;
- 2) based blinded data review, all those subjects who had baseline WHO scale=3 had no respiratory failure, and therefore leading quasi-complete separation on primary endpoint.

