## 2.2.2 Other Objectives

- To investigate the effect of asapiprant on inflammation markers of COVID-19 infection, including but not limited to interleukin (IL)-6, C-reactive protein (CRP), IL-10, tumor necrosis factor alpha (TNF- $\alpha$ ), IFN- $\gamma$ , interferon alpha (IFN- $\alpha$ ), IFN- $\gamma$ -induced protein 10 (IP-10), monocyte chemoattractant protein-1 (MCP-1), cluster of differentiation (CD)4+ and CD8+ T cells, and absolute lymphocyte count
- Determine peak and trough concentrations of study drug after first dose and at steady state and, if possible, develop a population PK model

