### **8.7.1.1 Statistical Analysis of Pharmacokinetic Parameters**

Single samples for PK analysis will be drawn at the time described in [Table 1](#). The times of dosing and sample collection are to be captured. Attempts will be made to develop a PK Population model based on the data. The results of the Population PK analysis will be published in a separate report.

Listing of individual PK concentrations and individual PK parameters of asapiprant will be based on the PK Analysis Sets. Individual concentrations and PK parameters of asapiprant will be listed and summarized by treatment with descriptive statistics (number, arithmetic mean, standard deviation [SD], coefficient of variation [CV%], median, minimum, maximum, geometric mean, and CV% of geometric mean). Figures of individual and mean ( $\pm$  SD) concentration-time profiles of asapiprant by treatments and study parts will be generated based on nominal time points.

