2.1 The Study Objectives

Primary Objective

QMS Document Name: Statistical Analysis Plan	Page 8 of 27
QMS No (include version ref): STF-015-GL.02	Document date: 09JUL2019
CONFIDENTIAL	

- To evaluate the efficacy of asapirant given by PO or NG administration versus placebo on the clinical signs and symptoms of COVID-19 infection in hospitalized patients ≥ 50 years of age.

Secondary Objectives

- To evaluate the ability of asapirant given by PO or NG administration to accelerate the clearance of the COVID-19 virus in patients with symptomatic disease requiring hospitalization.
- To determine the efficacy of asapirant by demonstrating improvement in COVID-19 illness and prevention of progression to RF using various endpoints.
- To evaluate the safety profile of asapirant given by PO or NG administration in patients ≥ 50 years of age hospitalized with COVID-19 infection.

Other Objectives

- To investigate the effect of asapirant on inflammation markers of COVID-19 infection, including but not limited to interleukin (IL)-6, C-reactive protein (CRP), IL-10, tumor necrosis factor alpha (TNF- α), interferon gamma (IFN- γ), interferon alpha (IFN- α), IFN- γ -induced protein 10 (IP-10), monocyte chemoattractant protein-1 (MCP-1), cluster of differentiation (CD)4+ and CD8+ T cells, and absolute lymphocyte count.
- Determine peak and trough concentrations of study drug after first dose and at steady state and, if possible, develop a population PK model.

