7. Time to clinical improvement from baseline value (defined by time to ≥ 1 -point improvement on WHO Ordinal Scale for COVID-19 score – must be maintained through Day 28)
8. Mean change from baseline in WHO Ordinal Scale for COVID-19 score at Day 14/End of Treatment, Day 28, Day 57
9. Incidence and duration of intubation
10. Length of intensive care unit stay (ICU)
11. Incidence and duration of supplemental O₂ administration
12. Incidence and duration of noninvasive ventilation or high-flow nasal cannula O₂ administration

13. Incidence and duration of mechanical ventilation
14. Incidence and duration of mechanical ventilation plus additional organ support using vasopressors, and/or renal replacement therapy and/or ECMO
15. Daily ratio of oxygen saturation (SpO_2) to fractional inspired O_2 ($\text{SpO}_2/\text{FiO}_2$)
16. Length of hospital stay
17. Incidence of re-hospitalization through Day 57
18. Proportion of patients requiring intensive care unit admission post randomization

Exploratory Endpoints

1. Inflammation markers including: IL-6, CRP, IL-10, TNF- α , IFN- γ , IFN- α , IP-10, MCP-1, and absolute lymphocyte count
2. Assess peak and trough concentrations of asapiprant at steady state
3. Assess PGD2 pre-diagnostic to assess correlation with response to treatment for COVID-19 based on change in the WHO Ordinal Scale for COVID-19 score

Safety endpoints

1. Incidence and severity of treatment-emergent AEs (TEAEs)
2. Safety outcome measure:
 - a. Occurrence of AEs
 - b. Laboratory safety parameters such as complete blood count, blood glucose, electrolyte, hepatic and renal functions taken before the first dose and on Days 2, 5, 14 and 28 and the time of discharge to find any changes or any systemic effect after treatment

3 Analysis Sets

Enrolled Analysis Set: all patients who provided informed consent.

Intent-to-Treat (ITT): all patients who have been randomized. The ITT will be used for efficacy endpoints. Patients will be analyzed according to the treatment group to which they were randomized. The ITT will be used for the primary efficacy analysis.

Modified Intent-to-Treat population (mITT): all ITT patients with exclusion of randomized untreated patients and randomized ineligible patients.

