4.1 General Statistical Methods

The statistical analyses will be presented by treatment group for the different analysis sets as defined in [section 3](#).

Summary tables will be structured with a column for each treatment in the order (asapiprant, Placebo, Total).

Continuous variables will be summarised using descriptive statistics, i.e., displaying number of patients in the respective analysis population, number of patients with data, mean, median, standard deviation (SD), minimum, and maximum.

Categorical variables will be summarised by using frequency counts and percentages. In addition, the number of patients with missing values will be displayed. Unless specified, the denominator for percentages will be the number of patients in the analysis set and treatment group under consideration.

Means and medians will be reported at 1 more significant digit than the precision of the data. Standard deviations and confidence intervals (CIs) will be reported at 2 more significant digits than the precision of the data. Minimum and maximum will be reported to the same level of precision as the original observations. Percentages will be presented to 1 decimal place if not otherwise stated.

QMS Document Name: Statistical Analysis Plan	Page 12 of 27
QMS No (include version ref): STF-015-GL.02	Document date: 09JUL2019
CONFIDENTIAL	

If the number of patients in a category is 0, then percentage will not be displayed, and only a count of 0 will be shown.

All p-values will be two-sided and reported to 4 decimal places at least. Values less than 0.0001 will be displayed as <0.0001.

In listings, data will be sorted by treatment, site, and patient ID, and when appropriate by visit or other identifiers for sequence or type of observation.

The confidence level for calculation of CIs will be chosen as (1-significance level) of the respective statistical test.

If a qualitative parameter in a table has missing values, a row with the number of missing values will be added.

Factor 365.2425 is used for duration conversions between days and years. Factor 30.436875 is used for duration conversions between days and months.

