4.7 Definition of Baseline Values

The baseline value is defined to be the last non-missing assessment prior to randomization. For baseline WHO ordinal scale, if not collected prior to randomization, the earliest collected WHO ordinal scale collected on the same day as randomization will be used as baseline. Pre-randomization assessments on the same day as randomization will be considered the baseline assessment for each of these respective study procedures. Unless otherwise specified, change from baseline calculations for a treatment window assessment will be the applicable treatment window assessment minus the

baseline assessment. If either the treatment window assessment value or the baseline value is/are missing, then change from baseline will be set to missing.

Age in years will be calculated as (date of informed consent – January 01 of year of birth) / 365.2425.

4.8 *Planned Analyses*

The following statistical analyses are planned for this study:

- Unblinded safety analyses for Data Monitoring Committee (DMC): An independent DMC will be utilized throughout the study to monitor patient safety. DMC meetings for safety will be conducted after 33, 100, and approximately 208 subjects complete assessments through the 28-day follow up (Day 28), approximately 14 days after the final dose of study drug. A DMC charter will be developed preceding study initiation and will define DMC processes and meetings, and required report contents.
- Interim analysis: An interim look for safety and primary endpoint will be conducted by the DMC when approximately 208 patients in the ITT population complete assessments through the 28-day follow up (Day 28), approximately 14 days after the final dose of study drug.

When all subjects enrolled under the targeted or adjusted sample size have completed the study through Day 28 (i.e., full study enrolment is completed), the clinical database will be cleaned, frozen, and an assessment of the primary efficacy endpoint and secondary, exploratory, and safety endpoints up to Day 28 in the ITT population will be created. Individuals involved with the conduct of the study will not have access to unblinded data until database lock. Final analysis: final analysis on efficacy and safety will occur after the database is locked.

4.9 *Multiple Comparison/Multiplicity*

No multiplicity adjustment is planned.

5 Study Population and Disposition

5.1 *Analysis Population*

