Mean change in WHO Ordinal Scale at Day 14, 28, and 57 will be analyzed using ANCOVA on change at each time point. The model will include the stratification factors. The least squares means (LS-means) for each treatment, LS-means treatment difference and corresponding CI for the LS-means difference and p-value for the treatment difference, will be reported at the Day 14, 28, and 57.

Results from Wilcoxon rank sum test and t-tests will also be reported for change in WHO Ordinal Scale at the Day 14, 28, and 57.

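### SAP 12 gives the exploratory inflammation markers raw-scale descriptive summaries only, with no between-arm estimate or interval, although the objective is worded as a treatment effect

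*SAP*

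**What the plan says.** The objective is among the 'Other' objectives (protocol 2.2.2, repeated in SAP 2.1): "To investigate the effect of asapiprant on inflammation markers of COVID-19 infection". The endpoint is the first exploratory endpoint (protocol 2.3.3, SAP 2.3).

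The whole analysis is in SAP 12: "summaries will be presented by treatment and overall using descriptive statistics. Both the observed value and the change from baseline value will be summarized". Two general sections give this its meaning:

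- SAP 4.1 defines the summary of a continuous variable as "number of patients with data, mean, median, standard deviation (SD), minimum, and maximum".
- SAP 4.7 defines change as a subtraction: "change from baseline calculations for a treatment window assessment will be the applicable treatment window assessment minus the" baseline assessment.

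Stronger tools are planned elsewhere. Protocol 8.7.1.1 summarises drug concentrations with "median, minimum, maximum, geometric mean, and CV% of geometric mean". SAP 10.2.3 compares arms by model: "Mean change in WHO Ordinal Scale at Day 14, 28, and 57 will be analyzed using ANCOVA on change at each time point". SAP 10.2.4 uses ANCOVA for the other continuous secondary endpoints. None of this reaches the markers.

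**The concern.** A question about the effect of a treatment calls for a contrast between arms with a measure of its uncertainty. SAP 12 provides neither; a reader would have to compare two columns of summaries by eye. The drug's rationale is immunomodulation (protocol 1.2.2 and 2.1), so these samples are the trial's main evidence on mechanism.

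The scale is a second, conditional matter. If concentrations such as IL-6 or CRP are strongly right-skewed, a few patients largely determine the mean, the SD and the mean arithmetic change. A proportional effect is then hard to see in those statistics.

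Two inconsistencies add to this. CD4+ and CD8+ T cells are in the objective but not in the SAP's endpoint list or analysis section. SAP 1 also places pharmacodynamic analyses outside the SAP, while SAP 12 summarises the markers.

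**Working it through.** **Is any between-arm estimate planned?** No figure in either document bears on this, so the check is of the text.

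- SAP 12: descriptive statistics by treatment and overall.
- SAP 4.1: no geometric mean, quartile, interval or test in the definition.
- SAP 4.7: change is a difference, not a ratio or a log difference.
- SAP 10.2.3 and 10.2.4: ANCOVA, t-tests and Wilcoxon tests for WHO-scale change and other continuous secondary endpoints only.
- Protocol 8.7.2 files the markers under pharmacodynamic analysis; 8.7.2.1, on statistical analysis of those parameters, has no text.
- Protocol 8.4 says the SAP will cover pharmacodynamic methods. SAP 1 excludes them. SAP 12 then summarises the markers and names a separate plan for pharmacokinetics only.

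So no between-arm estimate is planned in these documents.

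**CD4+ and CD8+ T cells.** They are named in protocol 2.2.2, 2.3.3 and 7.2.9 and in SAP 2.1. SAP 2.3 and SAP 12 omit them. SAP 1 gives the SAP precedence over the protocol. The SAP 12 list is worded as non-exhaustive, so it does not bar them, but the SAP 2.3 list lacks them without explanation.

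**How much could the scale matter?** This is an illustration only. From the documents: 312/2 = 156 per arm. Assumed: lognormal marker with median 1, log-SD s, baseline-to-visit correlation r on the log scale, and true ratio k = 0.70, so −ln k = 0.357.

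Approximate formulas:

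- Log ANCOVA: SE = s√(1−r²)·√(2/n); power ≈ Φ(0.357/SE − 1.96).
- Difference in mean raw change: d = (1−k)·exp(s²/2).
- Variance of raw change: placebo 2e^{s²}(e^{s²} − e^{rs²}); active e^{s²}[(e^{s²}−1)(1+k²) − 2k(e^{rs²}−1)]. Power ≈ Φ(d/SE − 1.96), where SE is the root of the summed variances over n.

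With s = 1.0, r = 0.5, n = 156:

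- Log scale: SE = 0.866 × 0.1132 = 0.0981; 0.357/0.0981 = 3.64; power ≈ Φ(1.68) = 95%. An observed ratio of 0.70 would have a 95% CI of 0.58 to 0.85.
- Raw change: d = 0.3 × 1.649 = 0.495; variances 5.81 and 4.49; SE = √(10.31/156) = 0.257; d/SE = 1.92; power ≈ Φ(−0.04) = 49%.

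Simulation (2,000 runs per setting, 156 per arm) agrees with this. Power for r = 0.3 / 0.5 / 0.7:

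| log-SD | raw-change t-test | Wilcoxon on raw change | log ANCOVA | share of squared deviation in raw change from the most extreme 5% |
|---|---|---|---|---|
| 0.5 | 99 / 100 / 100% | 100 / 100 / 100% | 100 / 100 / 100% | 41–42% |
| 0.8 | 70 / 79 / 93% | 83 / 91 / 99% | 99 / 99 / 100% | 56–59% |
| 1.0 | 42 / 52 / 68% | 60 / 74 / 92% | 90 / 96 / 99% | 66–69% |
| 1.5 | 15 / 15 / 21% | 33 / 41 / 60% | 62 / 67 / 84% | 84–86% |

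A separate run with r from 0.3 to 0.6 gave 68 to 87% against 98 to 100% at log-SD 0.8 and 156 per arm. At 75 per arm and log-SD 1.0 to 1.3 it gave 14 to 35% against 41 to 77%. The realised sample is not stated: the SAP addendum reports that enrolment stopped before the interim analysis, so 156 per arm is the planned size, not the analysed one.

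**The case against.** The case for leaving SAP 12 alone is reasonable. The markers are exploratory, under an 'Other' objective, and protocol 8.4 foresees describing other continuous outcomes. Description is a defensible minimum at that tier. The median is already planned and resists extremes. SAP 1 puts pharmacodynamic analyses elsewhere, so a separate plan cannot be ruled out. One model per marker per visit would produce many unadjusted intervals, and logs fail for values below quantification. All of this stands. It lowers the priority but does not supply the missing contrast: SAP 12 takes on the markers itself and names another plan only for pharmacokinetics.

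Two stronger readings are tempting, and the documents do not support them.

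- A reader might infer that the plan will report a treatment effect distorted by outliers. It plans no treatment effect at all, so there is nothing to distort. The sensitivity to high values applies to the mean, SD and mean change, and only if the markers are skewed. The documents give no marker distribution, and absolute lymphocyte count, a cell count, need not behave like a cytokine concentration.
- A reader might take the power figures as the chance that this SAP misses a real effect. They describe a raw-change t-test, which SAP 12 does not include, at assumed variability and at a sample size the trial may not have reached.

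**Conclusion.** The gap is confirmed on the text: an objective worded as a treatment effect has, in these documents, no between-arm estimate and no interval, only raw-scale summaries. The CD4+/CD8+ mismatch and the conflict between SAP 1, SAP 12 and the empty protocol 8.7.2.1 also stand without any assumption.

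The benefit of the log scale is conditional. It is negligible at log-SD 0.5, moderate at 0.8 and large at 1.0 or more, given lognormal markers, a proportional 30% reduction and the correlations assumed. Severity is minor: the endpoint is exploratory and no primary, secondary or safety conclusion depends on it.

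**What to change.** In SAP 12:

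- Add geometric means and geometric mean ratios to baseline by arm and visit, keeping the median.
- For each marker and visit, fit an ANCOVA on the log value with treatment, log baseline, region and age group. Report the ratio of geometric means with 95% CI, labelled exploratory and unadjusted for multiplicity.
- State that both randomised arms are used. The PD Set in SAP 3 contains only patients dosed with asapiprant, so it cannot support a comparison.
- State a rule for values below quantification, and how markers missing after death are treated.

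Elsewhere, either restore CD4+ and CD8+ T cells to SAP 2.3 and 12 or record why they were dropped and align SAP 2.1. Reconcile the exclusion of pharmacodynamic analyses in SAP 1 with SAP 12, and fill or remove protocol 8.7.2.1.

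The cost is a few lines of text and one standard model per marker and visit, with no new data. The drawback is more exploratory output with many unadjusted intervals.
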